With the proposed study treatment, it is expected that the median time to achieve hyperbilirubinemia normalization or at least a 50% reduction in peak total bilirubin will be shortened to 11 days for patients previously treated with PEG-asparaginase, and to 7 days for patients previously treated with inotuzumab. That is corresponding to a 20% increase in response rate (i.e. an increase from 30% to 50%) for each of the cohort of patients.

Simon's two-stage Minimax design³² will be implemented for each cohort of patients. The null hypothesis that the true response rate is 30% will be tested against a one-sided alternative 50%. In the first stage, 19 patients will be accrued. If there are 6 or fewer responses in these 19 patients, the study will be stopped. Otherwise, 20 additional patients will be accrued for a total of 39. The null hypothesis will be rejected if 17 or more responses are observed in 39 patients. This design yields a one-sided type I error rate of 0.05 and power of 80% when the true response rate is 50%. The expected sample size is 25.7 and the probability of early stop is 66.6% under the null hypothesis.

Analysis Plan:

The primary endpoint is bilirubin normalization or at least a 50% reduction in peak total bilirubin in patients treated with levocarnitine and vitamin B complex. Response rates will be estimated along with the 95% confidence interval. Secondary endpoints include tolerability of levocarnitine and vitamin B complex and chemotherapy dose intensity. Descriptive statistics will be used to summarize secondary endpoints. The incidence rates of binary secondary endpoints will be estimated, along with the 95% confidence intervals. The duration of time to hyperbilirubinemia normalization or at least a 50% reduction in peak total bilirubin will be estimated using the Kaplan-Meier method. For exploratory purposes, the time to hyperbilirubinemia normalization or achieving at least a 50% reduction in peak total bilirubin will be compared to historical controls using the Log rank test. Competing risk analysis will be considered in the case that patients died before bilirubin normalization or at least a 50% reduction in peak total bilirubin is achieved.

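### Does the planned 95% confidence interval contradict the one-sided 5% two-stage test at the success boundary of 17/39?

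*Combined protocol and SAP*

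**What the plan says.** The design is in Section 11.0, Statistical Considerations, of the combined protocol and SAP: "Simon's two-stage Minimax design³² will be implemented for each cohort of patients". The null response rate is 30% and the one-sided alternative is 50%. After 19 patients there is a futility look: "If there are 6 or fewer responses in these 19 patients, the study will be stopped". Otherwise the cohort goes on to 39 patients, and "The null hypothesis will be rejected if 17 or more responses are observed in 39 patients". The section states a one-sided type I error of 0.05, 80% power, an expected sample size of 25.7 and a 66.6% chance of stopping early under the null.

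The Analysis Plan in the same section has one sentence on reporting the primary endpoint: "Response rates will be estimated along with the 95% confidence interval". It does not give the sidedness of the interval, the method, the point estimator or any allowance for the first-stage stop. Nothing in the section makes success depend on the interval.

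**The concern.** A one-sided 5% test corresponds to a 90% two-sided interval, or to a one-sided 95% lower bound. The conventional reading of the plan's interval is two-sided, which is stricter at the lower end than the test. A cohort could then be declared positive while its published interval still includes 30%. In a single-arm cohort 30% is the only benchmark, so a reader could ask which statement to believe, and an interval level chosen after the data are seen would be open to criticism.

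The second worry is the estimate. Stopping for futility at 6 of 19 makes the plain proportion a biased estimator, and the plan does not name a corrected one.

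**Working it through.** **Inputs (Section 11.0):** n1 = 19, stop at 6 or fewer; n = 39, reject at 17 or more; p0 = 0.30, p1 = 0.50.

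**1. The plan's own figures.** P(reject | p) = sum over x = 7 to 19 of Bin(x; 19, p) × P(Bin(20, p) ≥ 17 − x).

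- p = 0.30: 0.0455 (stated 0.05)
- p = 0.50: 0.804 (stated 80%)
- Early stop under the null: P(Bin(19, 0.30) ≤ 6) = 0.6655 (stated 66.6%)
- Expected size: 19 + (1 − 0.6655) × 20 = 25.69 (stated 25.7)

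All four agree. A search over totals of 30 to 39 also returns 6/19, 16/39 as the minimax design.

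**2. Intervals at the boundary.** At 17/39 the proportion is 43.6% and the two-stage one-sided p-value is 0.0455, so the rule rejects. As an example, the Wald interval is 0.4359 ± 1.96 × √(0.4359 × 0.5641 / 39) = 0.4359 ± 0.1556. The two-stage exact lower 95% limit solves P(reach stage 2 and total ≥ 17 | p) = 0.025.

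| 95% interval at 17/39 | Limits |
|---|---|
| Clopper-Pearson | 27.8% to 60.4% |
| Wilson | 29.3% to 59.0% |
| Wald | 28.0% to 59.2% |
| Jeffreys | 29.0% to 59.1% |
| Two-stage exact | 28.1% to 61.1% |

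All include 30%, even the one adjusted for the design, so the cause is the confidence level and not the method. At 18/39 all exclude it (Clopper-Pearson 30.1% to 62.8%; two-stage exact 30.3% to 63.2%). The two-stage exact 90% interval at 17/39 is 30.3% to 58.6%, which agrees with the test.

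**3. How often it happens.** P(total exactly 17) = P(reject at 17 or more) − P(18 or more).

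| True rate | P(exactly 17/39) | P(reject) | Share of positive results |
|---|---|---|---|
| 30% | 2.3% | 4.55% | 50% |
| 40% | 10.1% | 35.6% | 28% |
| 45% | 11.0% | 59.9% | 18% |
| 50% | 8.1% | 80.4% | 10% |

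The 50% share in the first row is half of a 4.55% error that the design already allows.

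**4. Is an ordinary interval valid after the stop?** Clopper-Pearson was applied to whatever sample the cohort ended with (19 or 39) and weighted by the two-stage probabilities. At true rates from 20% to 60% in steps of 5 points, its coverage is 95.9% to 97.9%. It does not fall below 95%.

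**5. The estimator.** At 17/39 the uniformly minimum variance unbiased estimate (UMVUE) is the sum over x = 7 to 17 of C(18, x−1)·C(20, 17−x), divided by the sum of C(19, x)·C(20, 17−x). This gives 45.6%, against the plain 43.6%.

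| True rate | Bias, plain (points) | RMSE plain / UMVUE (points) | Mean if stage 2 reached, plain / UMVUE |
|---|---|---|---|
| 30% | −2.0 | 8.7 / 10.1 | 35.7% / 41.8% |
| 40% | −2.0 | 9.9 / 9.9 | 42.8% / 45.7% |
| 50% | −0.9 | 9.5 / 8.9 | 50.9% / 51.9% |

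The overall bias is downward. Among cohorts that reach 39 patients, the only ones that can be called positive, the plain proportion is already too high on average, and the UMVUE is higher still.

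**The case for a change.** The strongest case for a change is that 17/39 is the smallest result that counts as success, so the mismatch falls where interpretation is hardest. There are two cohorts: if they are independent with equal rates, the chance that at least one ends at 17/39 is 1 − (1 − 0.081)² = 15.6% at a true 50%, and 20.8% at 45%. Stating a 90% two-stage exact interval now would cost a sentence, would match the rule on both sides of the boundary (lower limit 30.3% at 17/39, 28.2% at 16/39), and would prevent a choice made after the result is known.

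Those figures stand, and such an interval could usefully be shown beside the 95% one. What does not stand is that the plan is wrong without it. The choice of a 90% or a 95% interval is a convention and changes no decision. At 17/39 the 95% interval errs on the cautious side and tells the reader that the result is borderline, which is true. Calling the interval two-sided is also an inference, since the text does not say so, and a one-sided 95% bound would agree with the test. The UMVUE would not remove the mismatch and has costs of its own: at the boundary it raises the reported rate by 2.0 points.

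**Conclusion.** No change is needed. The rule of 17 or more in 39 is the only decision criterion, it is unambiguous, and its stated operating characteristics are correct. A one-sided 5% test reported with a conventional 95% interval disagrees at a single outcome, with probability 8.1% per cohort if the true rate is 50% and 2.3% if it is 30%. The futility stop does not spoil the coverage of an ordinary Clopper-Pearson interval over the rates checked, and the plain proportion is off by about 1 to 2 points at 30% to 50%, against the treatment.

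The plan leaves the interval method and its relation to the rule unwritten. An analyst would fill this with an exact binomial interval, read as description beside the Simon decision, and the conclusion would be sound. This rests on the two-sided reading of the interval and on cohorts being analysed at the planned 19 and 39 patients.

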
treated with PEG^{4,7-9}. The high rates of hepatotoxicity limit the use of PEG in adults, therefore, assessing the efficacy of supportive therapy for its management is warranted.

Although hyperbilirubinemia is frequently reported in adult patients treated with PEG, determining risk factors associated with severe hyperbilirubinemia has been challenging due to the variations in protocols. Amongst the published protocols with PEG, there are differences in patients' age, stage of treatment, doses and frequency, and concomitant medications (e.g. anthracyclines). These variations have led to discrepancies in the reported incidence of hyperbilirubinemia. Age has traditionally been considered a risk factor for hyperbilirubinemia due to the poor tolerance among the adult patient population. Age cutoffs of both 40 and 45 years have been associated with increased induction mortality and toxicity in PEG-containing protocols^{4,5}. However, Douer et al. successfully administered PEG to patients up to 55 years of age with no deaths reported as a result of PEG toxicity⁹. Furthermore, advanced age was not associated with hyperbilirubinemia in patients treated on the MOAD protocol at our institution which included patients up to 69 years of age⁵. Patel et al. identified obesity as a risk factor for grade ≥ 3 (Tbili $> 3 - 10 \times \text{ULN}$) liver adverse events, with an increased risk for every 5 unit BMI increment (OR: 1.58, p=0.041)⁴. A retrospective analysis also identified patients with BMI ≥ 30 to be at an increased risk of grade ≥ 3 hepatotoxicity, and did not find age to be a risk factor¹⁰. Patients of Hispanic ethnicity, especially those with larger BMI, have also been reported to experience hepatotoxicity more frequently upon retrospective review¹¹. Specific comorbidities including type 2 diabetes mellitus and dyslipidemia have not been evaluated as risk factors for asparaginase toxicity, however like obesity, these are risk factors for non-alcoholic fatty liver disease, and consequently are worth investigating as risk factors for PEG-induced hyperbilirubinemia¹². Hypoalbuminemia is an indicator of nutritional status as well as the capacity of protein synthesis in the liver, and therefore may also be an indicator of poor PEG tolerance. Anecdotally, at our institution, we have observed significant hyperbilirubinemia in relapsed/refractory patients treated with PEG post allogeneic stem cell transplantation (alloSCT), potentially making transplant another risk factor. The mechanism in which PEG leads to hepatotoxicity is a result of protein derangements caused by glutamine deficiency and impairment of mitochondrial β -oxidation¹³⁻¹⁵. Glutamine depletion results in increased cellular stress and premature restoration of protein synthesis resulting in increased inflammation and cell death^{14,15}. Impaired mitochondrial β -oxidation prevents oxidation of long-chain fatty acids which results in fatty acid and triglyceride accumulation, leading to steatosis¹⁶. Evidence of steatosis has been reported in both pediatric and adult patients treated with asparaginase, indicating this toxicity is not limited only to adults^{17,18}. This protocol will investigate the use of levocarnitine for treatment of PEG-induced hyperbilirubinemia specified as Tbili $> 3 \times \text{ULN}$.

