5.0 Patient Eligibility

Inclusion Criteria:

1. Patients at least 12 years of age
2. Patients with a diagnosis of ALL who are receiving treatment with PEG-asparaginase or inotuzumab ozogamicin with Tbili >3xULN
3. Signed informed consent.

Exclusion criteria:

1. Pregnant or nursing women
2. Known hypersensitivity to levocarnitine or vitamin B complex

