7.0 Pretreatment evaluation

- 7.1 Informed consent
- 7.2 Baseline comprehensive metabolic panel (CMP)
- 7.3 Concomitant medications within 14 days of enrollment
- 7.4 Urine or serum pregnancy test for women of childbearing potential within 7 days of initiating chemotherapy

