11.0 STATISTICAL CONSIDERATIONS

This is an open label phase II study to evaluate the efficacy of levocarnitine and vitamin B complex for the treatment of hyperbilirubinemia ($Tbili > 3 \times ULN$) in adult patients with ALL treated with PEG-asparaginase or inotuzumab ozogamicin.

Two cohorts of patients will be enrolled in the study, patients who were previously treated with PEG-asparaginase and patients who were previously treated with inotuzumab. Evaluation for two cohorts of patients will be separated. Up to 39 patients will be enrolled for each cohort. Total sample size is up to 78.

The primary efficacy endpoint is response, which is defined as bilirubin normalization (TBili \leq 1.5 x ULN) or at least a 50% reduction in peak bilirubin level in 11 days for patients previously treated with PEG-asparaginase and bilirubin normalization (TBili \leq 1.5 x ULN) or at least a 50% reduction in peak bilirubin level in 7 days for patients previously treated with inotuzumab after initiation of the study treatment. All patients who receive at least 1 dose of levocarnitine will be assessed for safety. Patients must receive at least 5 consecutive days of levocarnitine to be considered evaluable for response.

Our retrospective data suggested that without any treatment the median time to bilirubin normalization (TBili \leq 1.5 x ULN) or at least a 50% reduction in peak bilirubin level was 21 days for patients previously treated with PEG-asparaginase, and the median time to achieve hyperbilirubinemia normalization (TBili \leq 1.5 x ULN) or at least a 50% reduction in peak bilirubin level was 14 days for patients previously treated with inotuzumab. Assuming that the time to normalization follows exponential distributions, then estimated failure rate (no normalization of grade \geq 3 hyperbilirubinemia or less than 50% reduction in peak total bilirubin) would be 70% at day 11 for patients previously treated with PEG-asparaginase and at day 7 for patients previously treated with inotuzumab, respectively. This corresponding to a response rate of 30%.

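### The exploratory log-rank comparison with historical controls is unadjusted and may be confounded by case severity, in either direction

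*Combined protocol and SAP*

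**What the plan says.** Section 11.0 Statistical Considerations plans two separately evaluated single-arm cohorts, one after PEG-asparaginase and one after inotuzumab. In each, the decision rests on a Simon minimax test of a 30% response rate against 50%. The cohort stops with 6 or fewer responders among 19; otherwise it continues to 39 and rejects the null at 17 or more.

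Time to response is a separate analysis. The Analysis Plan gives Kaplan-Meier estimates and then this comparison: "For exploratory purposes, the time to hyperbilirubinemia normalization or achieving at least a 50% reduction in peak total bilirubin" is set against historical data, the sentence ending "reduction in peak total bilirubin will be compared to historical controls using the Log rank test". It names no covariate, stratum, matching or weighting, and states no size or power.

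The controls appear only as medians. "Our retrospective data suggested that without any treatment the median time to bilirubin normalization" or to a halving of the peak "was 21 days for patients previously treated with PEG-asparaginase"; the inotuzumab figure is 14 days. Their number, calendar period, starting bilirubin and time zero are not given.

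Section 5.0 admits consenting patients "receiving treatment with PEG-asparaginase or inotuzumab ozogamicin with Tbili >3xULN", with no upper limit among the inclusion or exclusion criteria. Item 7.2 requires a baseline metabolic panel. Response in the trial is counted from the start of study treatment, which section 6.1 triggers at the same bilirubin threshold.

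**The concern.** A log-rank test compares two groups as they stand. Here one group is consenting trial patients and the other is a retrospective series, and nothing in the plan makes their severity alike. If more severe cases recover more slowly and the two groups hold different shares of them, the test measures that difference together with any drug effect.

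This is the only planned analysis that sets treated recovery times beside untreated recovery times, so a small p-value would be taken as support for faster recovery even under an exploratory label. The 30% null of the primary test was derived from the same retrospective medians, so a case-mix difference would reach that test too.

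**Working it through.** **1. The plan's own figures.** Inputs are from section 11.0.

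- Historical failure, exponential: 2^(−11/21) = 0.696 (PEG-asparaginase, day 11) and 2^(−7/14) = 0.707 (inotuzumab, day 7). Both match the stated 70%.
- Early stop at 30%: P(X ≤ 6 | n = 19) = 0.6655. Expected size: 19 + 20 × (1 − 0.6655) = 25.69.
- Rejection probability, Σ over x = 7 to 19 of P(X1 = x) × P(X2 ≥ 17 − x): 0.0455 at 30% and 0.8036 at 50%.

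All reproduce. The plan gives no figure for the log-rank comparison, so the rest is illustration under assumptions.

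**2. Continuous severity, no drug effect.** Assumed: 39 trial and 39 control patients, overall median 21 days, censoring at day 30, two-sided 5% test. Severity is N(0,1), with a mean shift between groups. Log time = constant + slope × severity + exponential error. The ratio of typical recovery times produced by case mix alone is exp(slope × shift). Ranges are across repeated runs of 1,200 to 4,000 trials per setting.

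| Slope | Shift (SD) | Time ratio | Unadjusted log-rank significant |
|---|---|---|---|
| 0.5 | 0.25 | exp(0.125) = 1.13 | 6–8% |
| 0.5 | 0.50 | exp(0.25) = 1.28 | 13–15% |
| 0.5 | 0.75 | exp(0.375) = 1.45 | 23–24% |
| 0.25 | 0.25 | exp(0.0625) = 1.06 | 5–6% |
| 0.25 | 0.50 | exp(0.125) = 1.13 | 7–8.5% |
| 0.25 | 0.75 | exp(0.1875) = 1.21 | 9–10% |

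A Cox model adjusted for the simulated severity stays at 4.8–5.3% throughout. For scale, the hoped-for effect is a time ratio of 21/11 = 1.91.

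**3. Two severity classes, no drug effect.** Assumed: 39 trial patients, 39 or 80 controls, control median held at 21 days, censoring at day 60, 3,000 runs. The nominal rate of falsely favouring the drug is 2.5%.

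| Recovery rate, severe v other | Severe: trial v controls | Falsely favours drug, unadjusted | Same, stratified |
|---|---|---|---|
| 0.5 | 30% v 50% | 8.5–10.3% | 2.6–3.0% |
| 0.5 | 20% v 60% | 20.8–26.4% | 2.5–2.9% |
| 0.7 | 30% v 50% | 5.2–6.6% | 2.3–3.1% |
| 0.5 | 30% v 30% | 2.7–2.8% | 2.7–2.9% |
| 0.5 | 60% v 20% | 0.1–0.2% | 2.5–3.2% |

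In the last row the unadjusted test falsely goes against the drug in 19.7–22.8%. When severity does not affect recovery, the unadjusted favourable rate is 2.2–3.8%.

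**4. Reach into the primary test.** Take the second row of that table. Write λ for the recovery rate of the less severe patients and x = exp(−10.5λ). A control median of 21 days requires 0.4x² + 0.6x = 0.5, so x = 0.596 and λ = 0.0492 per day. The trial's day-11 response with no drug effect is 1 − (0.8 × exp(−0.542) + 0.2 × exp(−0.271)) = 1 − (0.465 + 0.153) = 38%. The Simon design then rejects with probability 27.5%, against 4.55% at a true 30%.

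**The case against.** **The test is exploratory.** This is true and it limits the weight of the point. No decision, alpha or power rests on it.

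**A reader might take it as the trial's only evidence against untreated recovery.** It is not. The Simon test compares the response rate with a null built from untreated medians, and that is the main treated-versus-untreated comparison. A Cox model leaves it unchanged; only a table of starting severity bears on it.

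**A reader might conclude that a severity difference will be read as a drug effect.** The documents do not support this. It needs severity to predict recovery time and to differ between the groups, and neither is shown. The endpoint also offers some protection. With a peak above 3xULN, half the peak always exceeds 1.5xULN, so the 50% limb is met no later than normalization. The endpoint is in effect time to halving of the patient's own peak, and under proportional decline the starting level would not alter it. Severity could still act through slower clearance or a later peak: section 6.1 allows for patients with no improvement after two days of treatment. Whether it does is unknown.

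**A reader might assume that starting bilirubin is on file for both groups.** A baseline panel is required only for trial patients, and that it contains total bilirubin is its usual content, not spelled out. For the controls, serial values are a fair inference, because time to halving cannot be computed without them. A value at a defined time zero is not stated. If the control clock started elsewhere, for example at the peak, the covariate would mean different things in the two groups and adjustment could add bias. This objection stands, and it sets the order of the fix.

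**BMI.** Section 2.1 reports an "increased risk for every 5 unit BMI increment", but for developing grade 3 or higher liver events, not for recovery time afterwards. It gives little support for BMI as a covariate here.

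**The simulations** fix 39 trial patients. Without a drug effect a cohort stops at 19 with probability 66.6%, and that case was not run.

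**Conclusion.** The point holds in limited form. The exploratory comparison is unadjusted, entry severity is unbounded above, and the controls are undescribed, so it may be confounded by severity in either direction. The size cannot be derived from the documents. Under the assumed slopes of 0.25 to 0.5 and shifts of 0.25 to 0.75 SD, a nominal 5% test is significant in about 5% to 24% of trials with no drug effect. The lower settings are barely above nominal, and with equal case mix there is no material bias. The range illustrates and does not bound the effect, since slope, shift, control number and follow-up are all assumed.

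The adjusted analyses kept close to their nominal rates because they used the very variable that drove recovery. Real starting bilirubin is at best a proxy, so adjustment would reduce confounding without guaranteeing its removal. The primary design figures are arithmetically sound; what is open is whether a 30% null suits the patients enrolled.

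**What to change.** Add to the Analysis Plan, separately for each cohort:

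1. Describe the historical controls: number, period, selection and time zero. Set their time zero to match the trial's as closely as possible, for example the first total bilirubin above 3xULN, with trial treatment starting at that trigger.
2. Report a Cox model, trial versus historical, adjusted for log total bilirubin at time zero in multiples of ULN, with the hazard ratio and 95% CI. Show the unadjusted log-rank test beside it and keep both labelled exploratory.
3. Tabulate starting bilirubin in the two groups side by side. This also shows whether the 30% null suits the enrolled patients.
4. State whether the requirement of five consecutive days of levocarnitine, set for response evaluability, also restricts the time-to-response set. The plan does not say.

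BMI may be added where available, but is optional.

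The cost is analysis wording, a few lines of code and a return to the retrospective records; no new visits or patients are needed. The step fails if time-zero bilirubin cannot be retrieved for the controls, in which case the plan should say so and present the log-rank result with that limitation. One covariate costs slight precision, more so in a cohort that stops at 19.
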